6.3 Adverse Events Definition and Reporting

Adverse event means any untoward medical occurrence associated with the use of an intervention in humans, whether or not considered intervention-related.

An adverse event (AE) or suspected adverse reaction is considered "serious" if, in the view of either the investigator or sponsor, it results in any of the following outcomes: death, a life-threatening adverse event, inpatient hospitalization or prolongation of existing hospitalization, or a persistent or significant incapacity or substantial disruption of the ability to conduct normal life functions.

Protocol Number [Protocol Number](#) Version Date and Version #

This protocol presents minimal risks to the subjects and Unanticipated Problems Involving Risks to Subjects or Others (UPIRSOs), including adverse events, are not anticipated. In the unlikely event that such events occur, Reportable Events (which are events that are serious or life-threatening and unanticipated (or anticipated but occurring with a greater frequency than expected) and possibly, probably, or definitely related) or Unanticipated Problems Involving Risks to Subjects or Others that may require a temporary or permanent interruption of study activities will be reported immediately (if possible), followed by a written report within 5 calendar days of the Principal Investigator becoming aware of the event to the IRB (using the appropriate forms from the website) and any appropriate funding and regulatory agencies. The investigator will apprise fellow investigators and study personnel of all UPIRSOs and adverse events that occur during the conduct of this research project through regular study meetings.

6.4 Reaction Management

The stress induction procedure used in this minimal risk study is a physiological stressor, which disrupts the body's homeostasis via exposure to cold water. It is not designed to induce emotional stress responses and is unlikely to lead to adverse stress reactions in healthy populations, such as the one studied here. In the case of an emergency, psychologists at the Yale Stress Center (including PI [name]) may be contacted to speak to the participant.

6.5 Withdrawal Procedures

Participants who withdraw from the study before completion will be given the opportunity to ask questions about the study. The data collected from these participants will not be analyzed.

6.6 Locations/Facilities

Some behavioral studies will take place in Sheffield-Sterling-Strathcona (SSS) Hall ([name]) or [name] and some will be conducted online, on mTurk or Prolific.

The fMRI studies will take place in the FAS Brain Imaging Center in Dunham Lab ([name]) or BrainWorks ([name]).

7 Statistical Design

The general statistical approach involves examining differences in our outcome measures as a function of stress condition (i.e., whether participants experience acute stress prior to the learning task or not). Analyses will primarily be conducted with repeated-measures ANOVAs (rmANOVA) and t-tests where appropriate.

7.1 Sample Size Considerations

For the behavioral studies, we aim for an $N = 46$ per condition. This is consistent with the sample size of the study on which this behavioral experiment is based (Sherman & [name], 2020).

To determine the sample size for the fMRI study, we conducted power analyses based on our previous work demonstrating evidence of statistical learning in the hippocampus (Sherman et al., 2020). These results indicate that we would need $N = 40$ participants per group to detect neural effects ($d = .45$, 80% power). Thus, we will recruit 80 participants and randomly assign them to Stress ($N = 40$) or No Stress ($N = 40$) conditions.

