3.3 Objectives

The objective of this study is to leverage novel behavioral and neuroimaging assays to determine how stress modulates distinct hippocampal learning processes in humans. Using a between-subjects design, we will investigate whether exposure to a mild laboratory stressor changes the formation of different types of memories; specifically, storing individual experiences (episodic encoding) and learning environmental regularities (statistical learning). Our central hypothesis is that stress will modulate hippocampal responses and connectivity to enhance statistical learning while impairing episodic encoding. The following specific aims will be addressed:

Aim 1. Characterize how acute stress affects the relative expression of statistical learning and episodic encoding.

Aim 2. Identify the neural mechanisms by which stress influences statistical learning and episodic encoding.

As a secondary objective, we will determine whether individual variability in the magnitude of the stress response influences the effects of stress on hippocampal learning.

Protocol Number [Protocol Number](#) Version Date and Version #

4 Study Design

Overview

The in-lab experiments will consist of two testing sessions on two consecutive days. Sessions will occur between 12:00-6:00pm to account for circadian fluctuations in cortisol (Lupien et al., 2007). On Day 1, participants will be exposed to a stress or control manipulation followed by a learning task. On Day 2, participants will be tested for their memory. At the end of the experiment, the experimenter will answer any remaining questions from the participant.

Participants will provide multiple salivary samples over the course of the experiment. Saliva will be collected using salivettes, which participants will be instructed to hold under their tongue for two minutes. These will be stored in sterile tubes in a -20 freezer. The samples will be exclusively analyzed for cortisol and alpha-amylase concentrations.

Both behavioral and fMRI studies will follow the same overall design, which is described below.

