5.2 Number of Participants

Approximately five-hundred participants will be enrolled in the experiments. We plan to run between two and four behavioral studies ($N = 46-138$ each, depending on the exact parameters of the study) and one fMRI study ($N = 100$). These numbers were determined based on power analyses from past studies of statistical learning and episodic encoding (Sherman & [name] 2020) and acute stress effects on memory ([name] et al 2019).

Participants who do not meet our eligibility criteria as confirmed during recruitment (i.e., self-reporting that they are out of the age range or ineligible for MRI studies) will not be included in the participant count. For each participant who is excluded after their participation (i.e., due to responses on an intake questionnaire), we will recruit an additional participant so that the total number of usable participants matched the above-stated desired N s.

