We will test whether *stress induces state-level changes in TSP and MSP connectivity* by comparing background connectivity (Al-Aidroos et al., 2012) from CA1-entorhinal cortex (MSP) and CA1-CA2/3/DG (TSP) in Stress vs. No Stress participants. If state-level changes are not detected, we will use a different connectivity approach to separate connectivity patterns during different trial types. To probe the functional significance of connectivity changes, we will perform our recently developed seed connectome-based predictive modeling analysis ([name] et al., 2020), using whole-brain CA1 connectivity during encoding to predict subsequent memory performance in Stress and No Stress participants. To test whether *stress amplifies neural signatures of statistical learning*, we will use multivariate approaches to characterize neural evidence of prediction. Following prior work (Sherman & [name], 2020), we will train a classifier in the hippocampus (using a linear support vector machine implemented in Python's scikit-learn module) to distinguish between

Protocol Number [Protocol Number](#) Version Date and Version #

different scene categories. By training the classifier on voxel patterns in the hippocampus from the localizer run (in which no statistical regularities are present) to distinguish amongst B categories, we can derive a signature of B category to apply to learning runs. The extent to which B can correctly be classified during the preceding A item (when B has not yet been presented) serves as a neural measure of prediction. If stress amplifies neural signatures of statistical learning, we expect to see greater evidence for the predicted category in the Stress, relative to No Stress, group. Finally, univariate whole-brain analyses will include subsequent memory analyses (Wagner et al., 1998) (contrasting Remembered with Forgotten trials from conditions A/B/X) to *test how whole brain processes supporting memory differ* in Stress vs No Stress participants.

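### For the Stress vs No Stress fMRI comparison, 40 per group gives about 51% power at d = .45, not the stated 80%; 40 is close to the one-sample number

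*Combined protocol and SAP*

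**What the plan says.** Section 7.1 takes its fMRI effect size from earlier research by the same team: "we conducted power analyses based on our previous work demonstrating evidence of statistical learning in the hippocampus". It reports that "we would need $N = 40$ participants per group to detect neural effects ($d = .45$, 80% power"), and draws the allocation from this: "Thus, we will recruit 80 participants and randomly assign them to Stress ($N = 40$) or No Stress ($N = 40$) conditions". It does not name the test behind the calculation, the significance level or the sidedness.

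Section 3.3 describes the design: "Using a between-subjects design, we will investigate whether exposure to a mild laboratory stressor changes the formation of different types of memories". The fMRI tests in section 7.2 follow that design. Background connectivity is compared for the two hippocampal pathways, "MSP) and CA1-CA2/3/DG (TSP) in Stress vs. No Stress participants". For the classifier measure of prediction, "we expect to see greater evidence for the predicted category in the Stress, relative to No Stress, group". The whole-brain subsequent-memory analysis is also a comparison of the two groups. The primary neural hypotheses in section 4.2.1 (CA1–CA3 connectivity lower and CA1–entorhinal connectivity higher after stress) are likewise group differences.

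The Synopsis and section 5.2 give another total: "one fMRI study ($N = 100").

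**The concern.** A per-group number offered as the reason for a 40:40 randomisation should be the number needed to compare the two groups. An effect of d = .45 is moderate, and 40 per arm is well below what a two-sample test of such an effect usually needs.

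The source of the effect size adds to the doubt. As section 7.1 describes it, the earlier work showed that hippocampal statistical learning exists. It did not estimate how far stress changes it. These are different quantities. If the control group shows an effect of 0.45 SD and both groups have the same SD, a between-group d of .45 means that stress either abolishes the effect or doubles it (0.45 + 0.45 = 0.90).

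Aim 2 rests on these contrasts. A null result invites the reading that a study with 80% power found nothing, when the test would have missed a true d of .45 about half the time. Power also affects which analyses are run: section 7.2 turns to a second connectivity approach if the first detects no state-level change. Finally, with totals of both 80 and 100 in the protocol, the planned fMRI sample is not one number.

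**Working it through.** **Inputs.** From section 7.1: d = .45, target power 80%, 40 per group, equal allocation. From the Synopsis and section 5.2: total 100, taken here as 50 per group (the equal split is an assumption). Alpha is not given; two-sided 5% is assumed, with one-sided 5% alongside. There is no inflation for dropout, because sections 5.2 and 7.7 replace excluded participants. There is no adjustment for multiple tests.

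**Step 1: find a test that reproduces the plan's figure.** For a one-sample or paired t-test, the normal approximation is

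n = (1.960 + 0.842)² / d² = 7.849 / 0.2025 = 38.8.

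The exact noncentral-t solution is 40.7, so 41. At n = 40 the noncentrality is 0.45 × √40 = 2.85 on 39 degrees of freedom, and power is 79.3%. This agrees with 40 at 80%.

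**Step 2: the planned comparison.** For two independent groups,

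n per group = 2 × (1.960 + 0.842)² / d² = 2 × 7.849 / 0.2025 = 77.5, so 78.

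The exact t solution is 78.5, so 79 per group or 158 in total. At 40 per group the noncentrality is 0.45 × √(40/2) = 2.01 on 78 degrees of freedom. The normal approximation to power is Φ(2.012 − 1.960) = 52.1%; the exact value is 51.1%.

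**Step 3: vary the assumptions** (exact t, d = .45).

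| Two-sample setting | Power, 40 per group | Power, 50 per group | n per group for 80% |
|---|---|---|---|
| Two-sided 5% | 51.1% | 60.6% | 79 |
| One-sided 5% | 63.7% | 72.2% | 62 |
| Two-sided 20% | 76.5% | – | 45 |

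Even at a two-sided alpha of 20%, 40 per group does not reach 80%.

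**Step 4: what the planned sizes can detect.** The smallest d with 80% power at two-sided 5% is roughly (1.960 + 0.842) × √(2/n). That is 0.63 for n = 40 and 0.56 for n = 50; the exact t values are 0.634 and 0.566. One-sided 5% at 40 per group gives 0.56.

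**Step 5: repeated measures.** Section 7 names repeated-measures ANOVA as well as t-tests. Suppose d is scaled to the SD of a single measurement and r is the within-person correlation.

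- Group-by-condition interaction, effective d = 0.45 / √(2(1 − r)), 40 per group: power is 39% at r = 0.3, 51% at 0.5, 73% at 0.7 and 80% at 0.75.
- Group difference in the mean of m = 2 or 3 measures, effective d = 0.45 / √((1 + (m − 1)r)/m), with r from 0.3 to 0.7: power is 58% to 78%.

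**Step 6: the two totals.** Section 5.2 says exclusions are replaced so that the usable number meets its stated sizes. Its 100 is therefore not the 80 of section 7.1 plus an allowance for losses.

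**The case against.** The strongest reply is that section 7.1 never says the Stress vs No Stress contrast has 80% power. It speaks of detecting neural effects, using an effect size from work that showed such effects exist. Read literally, 40 per group is about right for finding the effect within each group, and nothing was miscalculated. That reading is possible. But the next sentence uses the figure to fix the size of a two-arm randomised study, and the tests in section 7.2 compare the arms. If the within-group reading is right, the planned contrasts have no power justification at all, and the text still has to change.

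Three narrower points deserve weight.

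- The one-sample origin is inferred from the numerical match and the source of the effect size; the protocol does not name the test. The shortfall does not depend on that inference.
- Alpha is not stated and the hypotheses are directional. One-sided testing raises power to 63.7%, which does not close the gap.
- A repeated-measures analysis could reach 80%, but among the cases tried only an interaction with a within-person correlation near 0.75 did so. The protocol gives no such correlation. Section 7.2 assigns repeated-measures ANOVA to behavioural hypotheses and describes the connectivity and classifier tests as group comparisons.

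The protocol also has no rule for interpreting a null neural result, so the risk of misreading one is a foreseeable consequence, not something the plan commits to. The conflict between 80 and 100 is a separate consistency error and adds nothing to the power argument.

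**Conclusion.** The concern holds. For the Stress vs No Stress comparison at d = .45, 40 per group gives 51.1% power (two-sided 5% t-test), and 80% would need 79 per group. One-sided 5% gives 63.7% and needs 62 per group. The larger total of 100, split equally, gives 60.6% two-sided. No conventional two-sample calculation supports the stated figure, whereas a one-sample or paired test fits it closely. The exact percentages rest on the assumed alpha, a simple two-group t-test and equal allocation; the conclusion survives one-sided testing and the larger total. An unstated and favourable repeated-measures correlation could change it. Because this is the only quantified power statement in the protocol and it does not apply to the planned fMRI contrasts, it must be corrected.

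**What to change.** Rewrite the fMRI paragraph of section 7.1 for the two-group comparison, naming the test, alpha and sidedness. At two-sided 5%:

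- with 40 per group, 80% power at d = 0.63 and about 51% at d = .45;
- with 50 per group, 80% power at d = 0.57 and about 61% at d = .45.

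Say that the combination of 40, d = .45 and 80% applies only to detecting a neural effect within a group, and that d = .45 is not an estimate of a stress-induced difference. If a repeated-measures test is the intended basis, state the contrast and the assumed within-person correlation. Choose one fMRI total, 80 or 100, and use it in the Synopsis, section 5.2 and section 7.1.

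The cost is protocol wording and a less favourable power statement. The correction itself requires no additional participants.

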Aim 1. Characterize how acute stress affects the relative expression of statistical learning and episodic encoding.

Aim 2. Identify the neural mechanisms by which stress influences statistical learning and episodic encoding.

As a secondary objective, we will determine whether individual variability in the magnitude of the stress response influences the effects of stress on hippocampal learning.

Study Population

Participants in this study will be healthy individuals aged 18-45. We aim to study this healthy cohort in order to understand the baseline relationship between stress and memory in neurotypical individuals.

Number of Participants

Approximately five-hundred participants will be enrolled in the study. We plan to run between two and four behavioral studies ($N = 46-138$ each, depending on the exact parameters of the study) and one fMRI study ($N = 100$). These numbers are based on power analyses from similar behavioral and fMRI studies (Sherman & [name], 2020).

Study Design

In this two-day study, participants will be exposed to a series of displays (e.g., scene images) and subsequently be tested on their memory for these displays. Some participants may undergo a stress manipulation, known as the cold pressor test (described below). Some participants may also undergo fMRI, so we can analyze how brain response patterns associated with learning and memory change as a function of stress exposure. Please see sections 4 and 6 for more detailed information about the study design and methodology.

Study Duration

We expect the total duration of the study to last 2-3 years. Each participant will participate in two sessions. The first session will take 1-2 hours and the second session will take 0.5-1 hour.

Outcome Variables

Protocol Number [Protocol Number](#) Version Date and Version #

The primary outcome variables will be performance on the behavioral learning and memory tasks. Additionally, we will examine cortisol and alpha-amylase responses to stress. In the fMRI study, we will additionally examine neural correlates of learning and memory.

Locations/Facilities

Some behavioral studies will take place in Sheffield-Sterling-Strathcona (SSS) Hall ([name]) or [name] and some will be run online (on mTurk or Prolific). The fMRI studies will take place in the FAS Brain Imaging Center in Dunham Lab ([name]) or BrainWorks at [name].

Abbreviations

Abbreviation	Explanation

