7.7 Handling of Missing Data

All data will be collected and stored electronically. Data will be missing only in the case of a technological failure (e.g., a computer error). Participants with incomplete datasets will be excluded from the analyses and replaced.

8 Data/Specimen Handling and Record Keeping

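### The fMRI study has two sample sizes, 100 usable participants in the synopsis and 5.2 and 80 recruited in 7.1, and the power statement in 7.1 fits only a within-group test.

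*Combined protocol and SAP*

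**What the plan says.** The protocol plans a single fMRI study and gives its size three times.

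- Synopsis, Number of Participants: "and one fMRI study ($N = 100$). These numbers are based on power analyses from similar behavioral and fMRI studies".
- Section 5.2 repeats the figure, "one fMRI study ($N = 100", and attributes its Ns to power analyses from earlier work on statistical learning and on acute stress effects on memory. It then says that anyone excluded after taking part is replaced so that "the total number of usable participants matched the above-stated desired" Ns.
- Section 7.1 bases the fMRI size on a power analysis of the group's earlier hippocampal work. It arrives at 40 "participants per group to detect neural effects ($d = .45$, 80% power" and concludes: "Thus, we will recruit 80 participants and randomly assign them to Stress" (40) or No Stress (40).

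Two other sections bear on losses. Section 7.7 says "Participants with incomplete datasets will be excluded from the analyses and replaced". Section 6.5 says of people who withdraw that "The data collected from these participants will not be analyzed" and does not mention replacement. No section gives a loss rate, an alpha level or the sidedness of the tests.

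**The concern.** All three statements are current text about the same study, and at least one must be wrong. A team that stops at 80 and a team that goes on to 100 could each cite the protocol. No interim analysis is planned, so nothing else fixes the end of enrolment. The precision of the Stress vs No Stress comparisons in 7.2 depends on which total is meant.

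Reconciling the totals also means saying what the chosen N is powered for. Section 7.1 is the only place that shows an fMRI effect size, power and group split. It does not name the contrast to which d = .45 applies, whereas most of the fMRI comparisons in 7.2 are between groups.

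**Working it through.** **Inputs.** From the synopsis and 5.2: N = 100. From 7.1: 40 per group, 80 in total, d = .45, 80% power. Assumed because the documents do not say: two-sided alpha 0.05, and an equal split of 100 into 50 + 50.

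**1. Reproduce the figure in 7.1.**
- One-sample (within-group) test: n = ((1.960 + 0.842)/0.45)² = 38.8, so 39 by the normal formula. The t-based solution is 40.7, so 41. Power at n = 40 is 79.3%. The stated 40 is reproduced to within one or two participants.
- Two-sample test: n per group = 2 × ((1.960 + 0.842)/0.45)² = 77.5, so 78. The t-based solution is 78.5, so 79. A one-sided 0.05 test needs 62. The stated 40 is not reproduced.

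The total of 80 is therefore 2 × 40, with 40 matching a test inside one group.

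**2. Size of the conflict.** 100 − 80 = 20 participants, and 20/80 = 25% of the figure in 7.1.

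**3. Precision of a group difference.** The 95% half-width in SD units, by normal approximation, is 1.96 × √(2/n).
- n = 40 per group: 1.96 × √(2/40) = 0.438.
- n = 50 per group: 1.96 × √(2/50) = 0.392.
- Ratio: √(50/40) = 1.118, so about 12% wider at 80. This ratio needs no effect size.

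**4. Power for Stress vs No Stress, if d = .45 is meant for that contrast** (two-sample t test).

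| Total N | Per group | Power, two-sided | Power, one-sided | d detectable with 80% power, two-sided |
|---|---|---|---|---|
| 80 | 40 | 51% | 64% | 0.63 |
| 100 | 50 | 61% | 72% | 0.57 |

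Neither total reaches 80% at d = .45 on either sidedness.

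**5. Can 100 be 80 plus losses?** The arithmetic requires a 20% loss, since 80/(1 − 0.20) = 100. Other rates give other totals: 89 at 10%, 95 at 15%, 107 at 25%. No section states any rate. The text also runs against this reading: 5.2 ties its Ns to usable participants, 7.7 replaces incomplete datasets, and 7.1 calls 80 the number to recruit.

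**The case against.** The best defence is that 100 is the number enrolled and 80 the number analysed. It has some support. Section 5.2 opens with "Approximately five-hundred participants will be enrolled in the experiments", and 6.5 drops withdrawn participants' data without saying that they are replaced. The replacement rule in 5.2 also illustrates exclusion only with intake-questionnaire responses. But the defence needs a 20% loss that no section states, and 5.2 and 7.7 deal with losses by replacement. Someone who withdraws before completion would ordinarily leave an incomplete dataset, which 7.7 replaces, although 7.7 attributes missing data to technical failure. The defence remains conceivable but is not what the text says.

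A reader might also infer more than the documents support, in three ways:

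- *That the protocol never says whether its Ns are enrolled or usable.* For 100 it largely does, through the replacement rule in 5.2. The unlabelled figure is the 80 in 7.1, described only as a number to recruit.
- *That the missing loss allowance is itself a fault.* A design that replaces losses does not need one.
- *That the 80/100 conflict costs 9.5 points of power.* This is the difference between 51.1% and 60.6%, and it holds only if d = .45 is a between-group effect, which no section says. Under the same assumptions the difference is about 2.5 points at d = 0.2 and 5.5 at d = 0.3. As a within-group test at d = .45, power is 79% at 40 and 88% at 50.

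Two further objections are fair. The one-sample versus two-sample question would remain if every section gave the same N, so it should not be used to make the conflict look larger. And since the synopsis and 5.2 attribute their Ns to power analyses of cited studies, a separate basis for 100 cannot be ruled out. That attribution does not reconcile 100 with 80.

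**Conclusion.** The point holds and should be fixed, but it is not fatal. The protocol sets two targets for one study, 20 participants apart, and no section links them. The consequence that rests on least is precision: intervals for a group difference are about 12% wider at 80 than at 100, assuming equal groups.

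Separately, the 80% power in 7.1 is right to within a point for a one-sample test at two-sided 0.05, and does not carry over to Stress vs No Stress at d = .45 under either total. The documents do not say which contrast was intended, so this is a statement to clarify and not proof that the calculation was wrong for its purpose. Neither N invalidates the planned comparisons.

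**What to change.** State one fMRI N and its per-group split in the same words in the synopsis, 5.2 and 7.1. Label it as usable participants, in line with the replacement rule in 5.2, or as enrolled if that is what is meant. In 7.1, restate the power or the detectable effect for that N, naming the contrast (within-group or Stress vs No Stress), alpha and sidedness.

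The cost is text edits in three places. No loss allowance has to be added, and no enrolment beyond the totals already stated is required. Choosing 100 commits to 20 more scans than 7.1 does, and choosing 80 accepts the wider intervals. If d = .45 is kept for the between-group contrast, the restated power will fall below 80% at either total. Reporting the detectable effect instead (d = 0.63 at 40 per group, 0.57 at 50, two-sided 0.05) would state plainly what the study can show.
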